### **INTRODUCTION**

#### **Purpose of statistical analysis plan**

The purpose of this document is to provide details of the statistical analyses and presentation of results to be reported within the principal paper(s) of the WAIT trial. Subsequent papers of a more exploratory nature (including those involving baseline data only) will not be bound by this strategy but will be expected to follow the broad principles laid down in it. Any exploratory, post-hoc or unplanned analyses will be clearly identified in the respective study analysis report.

The structure and content of this document provides sufficient detail to meet the requirements identified by the International Conference on Harmonisation (ICH) and the PCTU SOP (PCTU/07).

The following were reviewed in preparation for writing this document:

Trial protocol version 7 24/06/2011

ICH E9 Guidance on statistical principals for clinical trials

ICH E3 Structure and content of clinical study reports

CONSORT guidelines for the reporting of randomised trials

PCTU\_DM\_04 Standard Operating Procedures (SOP) for: Data Entry, Quality Control, Data Extraction and Database lock

## **Members of the writing committee**

[name] (CR) was primarily responsible for (i) writing the Statistical Analysis Strategy and (ii) writing the computer code implementing the analysis strategy and (iii) implementing the strategy at the point of analysis all under the guidance of [name] (SE).

This document has been developed prior to examination of trial data and will not be implemented prior to final approval and after the database has been locked to changes.

## **STUDY OBJECTIVES AND ENDPOINTS**

### **Study objectives**

#### **Primary objectives**

1.To determine whether intermittent treatment with oral montelukast in preschool children reduces the need for unscheduled medical attention (GP visit, hospital attendance, hospital admission) for wheeze.

#### **Secondary objectives**

2.To determine whether the effect of treatment on the primary analysis is different depending upon ALOX5 status (5/5 vs. 5/x and x/x).

3.To determine whether intermittent treatment with oral montelukast in preschool children reduces the time to first medical attendance.

4.To determine whether intermittent treatment with oral montelukast in preschool children reduces the need for each type of medical attention for wheeze: hospital admissions; hospital attendance; and GP visits.

5.To determine whether intermittent treatment with oral montelukast in preschool children reduces the time to first occurrence of each type of medical attention for wheeze: hospital admissions; hospital attendance; and GP visits.

6.To determine whether intermittent treatment with oral montelukast in preschool children reduces the duration of hospital admissions.

7.To determine whether intermittent treatment with oral montelukast in preschool children reduces the number of episodes, duration and time to first event of wheeze and cold.

8.To determine whether intermittent treatment with oral montelukast in preschool children reduces the need for alternative medications (Steroids, Salbutamol).

9.To describe the safety profile of montelukast.

10.To describe parents opinion of treatment efficacy

11.To describe compliance to medication

12.To determine whether baseline urinary eicosanoid level is different across baseline groups: ALOX5 status (A or B), leukotriene genes and, type of wheeze (episodic, multitrigger). **NOTE ANALYSIS DETAIL NOT CONTAINED IN THIS PLAN**

13.To determine whether montelukast is cost effective. **NOTE ANALYSIS DETAIL NOT CONTAINED IN THIS PLAN**

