#### Investigational Medicinal Product (IMP) usage:

- The number of IMP initiations (whether for wheeze or cold).
- Mean sachets (IMP use) per episode (wheeze or cold) as recorded on the diary card
- Compliance calculated from diary card, number dispensed and number returned

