## **Derived and computed variables**

All derived and computed variables will be documented in the analysis programmes. The primary outcome is a summation of all types of medical attendances across the entire trial, for each participant.

The primary outcome, and the breakdown of unscheduled medical opinion, will be taken solely from the phone call data as this data has been confirmed against clinical records.

Medication use data may be recorded on either the phone call CRF and/or the diary card. A medication will be defined as being used if it appears in either of these two records.

Medical attendance data was collected strictly within 12 months, as calculated from the date of randomisation. Participants who do not experience an event are censored at exactly 12 months of follow up or the point of withdrawal from follow up. Any diary data collected outside of the 12 month follow up will be excluded from the analysis. Participants who do not experience episodes of cold or wheeze will be censored at the point of 12 months from randomisation or withdrawal from medication, as diary cards are not completed for those not taking IMP.

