**Table 5: Time to first event of unscheduled medical attendance, wheeze or cold**

---

ITT population	Montelukast N=	Placebo N=	HR (95% CI)	p-value
----------------	-------------------	---------------	-------------	---------

---

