**Time (in days) to first:**  
**Hospital admission**  
**Hospital attendance (A&E or admission)**  
**Unscheduled GP visit**  
**Episode of wheeze**  
**Episode of a cold**

---

Data are median (IQR)

Data are analysed using a Cox regression model with fixed effects for stratification factor and treatment group

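### Time to first cold (objective 7, Table 5) is tested as an efficacy outcome, although a cold that is the child's first trigger for IMP begins before any dose in either arm

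*SAP*

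**What the plan says.** The treatment is intermittent. The primary objective reads "To determine whether intermittent treatment with oral montelukast in preschool children reduces the need for unscheduled medical attention", and the secondary objectives use the same description. Objective 7 extends the efficacy question to whether treatment "reduces the number of episodes, duration and time to first event of wheeze and cold". The Secondary outcomes section lists number, time to first episode and duration for colds as well as for wheeze, all from the diary card.

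Three statements bear on when IMP is taken:

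- Under IMP usage, one outcome is "The number of IMP initiations (whether for wheeze or cold".
- The next is "Mean sachets (IMP use) per episode (wheeze or cold) as recorded on the diary card".
- Under Derived and computed variables, children without a cold or wheeze episode are "censored at the point of 12 months from randomisation or withdrawal from medication", "as diary cards are not completed for those not taking IMP".

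Table 5, titled "Time to first event of unscheduled medical attendance, wheeze or cold", has a row "Episode of a cold" with columns for HR, 95% CI and p-value. Its footnote specifies a Cox model with stratum and treatment as fixed effects.

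The two lists in Analysis of secondary outcomes (Definition of outcome measure, and Secondary analysis) name first wheeze but not first cold. They also omit the number and duration of colds.

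**The concern.** A drug taken only once symptoms have begun cannot change when the first symptoms begin. If a child's first reason to start IMP is a cold, the time from randomisation to that cold is untreated time in both arms. A hazard ratio for it compares two groups of children who have not yet been dosed.

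The SAP nevertheless poses this as an efficacy question and reserves a p-value for it. A ratio near 1 could be read as evidence that montelukast has no effect on the time to first cold. A significant ratio would most likely be chance, and Multiple comparisons and multiplicity applies no adjustment while committing to report every comparison. Neither result would answer the question in objective 7.

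**Working it through.** The SAP gives no figure for objective 7, so there is none to reproduce. The check is a reading of the text, followed by illustrations on stated assumptions.

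**Step 1: when is the first dose?** IMP initiations are counted by reason, wheeze or cold, and sachets are counted per wheeze or cold episode. The diary sentence ties diary completion to taking IMP. Together with intermittent use, these imply that a course is started in response to a cold or wheeze. No sentence in the SAP states this as a rule, so it is an inference.

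**Step 2: first trigger is a cold.** Onset comes before the first dose in both arms. The true HR is 1.00, and a two-sided 5% test rejects 5% of the time.

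**Step 3: first trigger is wheeze.** The child may be treated for wheeze and have a first cold later. That cold follows exposure and could respond. Let *s* be the share of children whose treated wheeze comes before their first cold, and let the drug multiply their later cold rate by 0.67. The 33% is borrowed from Sample size determination, where it refers to attacks requiring medical attention. With constant rates and no 12-month cut-off, mean time to first cold is multiplied by (1 − s) + s/0.67, so the rate ratio is the inverse:

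- s = 0.1: 1/(0.9 + 0.149) = 0.95
- s = 0.3: 1/(0.7 + 0.448) = 0.87
- s = 0.5: 1/(0.5 + 0.746) = 0.80

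A simulation with follow-up cut at 12 months and an assumed 3 colds per year gave:

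| s | First-cold rate ratio |
|---|---|
| 0 | 1.00 |
| 0.1 | 0.96 |
| 0.3 | 0.89 |
| 0.5 | 0.82 |

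If the drug has no effect on later colds, the ratio is 1.00 at every *s*. The model favours the drug, because the effect lasts from the first treated wheeze to the end of follow-up although treatment is intermittent. The SAP gives neither *s* nor the cold rate.

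**Step 4: first wheeze.** A wheeze that begins before any dose is also beyond the drug's reach, but one that follows a treated cold is not. If *f* is the share of first wheezes that begin before any dose, and the effect is 0.67 in the rest, then approximately HR = f + 0.67(1 − f):

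- f = 0.2: 0.2 + 0.536 = 0.74
- f = 0.5: 0.5 + 0.335 = 0.84
- f = 0.7: 0.7 + 0.201 = 0.90

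The SAP does not give *f*, so these values show the direction of the pull and do not estimate its size.

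**Step 5: text against shell.** First cold appears in objective 7, in Secondary outcomes and in Table 5, but in neither analysis list. Under the lists it is not analysed; under the shell it is tested.

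**The case against.** The best reply is that the start rule is not written in the SAP. The diary sentence explains why follow-up is censored at withdrawal from medication and does not govern dosing. That is a fair caution, and the inference should be checked against the protocol. But no other reading fits an intermittent treatment whose initiations are classified by wheeze or cold.

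Second, the first-cold HR is not exactly 1 whatever the drug does, because children treated first for wheeze can have a later cold under or after IMP. This stands, and it is why the claim is null or nearly null rather than null by design.

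Third, a reader might extend the argument to the number of colds and conclude that its IRR should go too. The SAP does not support that. Only onsets before the first initiation are untreated. Later colds within the 12 months can follow exposure, so the 12-month IRR is a valid randomised comparison. Cold duration is likewise a proper target.

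Fourth, a reader might call the first-wheeze HR invalid. It is not. Counted from randomisation under intention to treat, it estimates the effect of the intermittent strategy, and wheeze before first use belongs to that strategy. It needs a note on interpretation only.

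Finally, the omission of first cold from the analysis lists does not show that the authors saw this problem, since those lists omit every cold outcome. It shows only that the text and the shell disagree.

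**Conclusion.** The point holds for one secondary comparison. Time to first cold cannot show whether montelukast affects time to first cold, because in children whose first trigger is a cold the event precedes treatment. The expected ratio is 1.00 if every first trigger is a cold. Under the favourable assumptions above it is about 0.96 with 10% treated first for wheeze. It reaches 0.82 only if half are, and if the effect on colds then persists to the end of follow-up. The conclusion rests on the inference that IMP is started in response to symptoms.

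The objective and table shell also conflict with the analysis lists. The primary outcome is not touched, and neither the number-of-colds IRR nor the first-wheeze HR is invalidated.

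**What to change.** 1. Remove time to first cold from the efficacy claim in objective 7.
2. In Table 5, show the first-cold row descriptively or label it a balance check, with no efficacy HR or p-value. Bring Secondary outcomes and the two analysis lists into line with this.
3. Keep the number-of-colds IRR, cold duration and the first-wheeze HR from randomisation. Beside the first-wheeze HR, note that onsets before the first IMP dose cannot reflect treatment and pull the ratio toward 1 by an amount the SAP does not allow to be calculated.
4. Optionally, add a supportive comparison by arm, adjusted for genotype. Among children whose first diary episode began as a cold without wheeze, compare the proportion who wheeze within a fixed window from its onset, set before unblinding. The window must not close when the episode ends, because treatment can change episode duration and so the time in which wheeze would count. Two limits should be stated: colds for which IMP was not started may be missing from the diary, and wheeze on the first dosing day is ambiguous.

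The cost is some SAP wording, one table row and one planned secondary p-value. The optional model uses diary fields already collected but only the children with a qualifying first episode.

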### **Exploratory objectives**

14.To determine whether the effect of treatment on the primary analysis is different depending upon ALOX5 status (categorised as (5/5 vs. 5/x) vs. x/x).

### **Outcome measures**

#### **Primary outcomes**

The number of times a child attends for an unscheduled medical opinion (a summation of hospital admissions, attendances, GP visits,) with respiratory problems over a 12 month period as confirmed from clinical records

#### **Secondary outcomes**

#### **Breakdown of unscheduled medical opinion**

Hospital admissions:

- Number of hospital admissions over the 12 month period as recorded at each phone call
- Duration of hospital admissions as recorded at each phone call
- Time from randomisation date to date of first hospital admission as recorded at each phone call

Hospital admission for wheeze:

- Number of hospital admissions over the 12 month period as recorded at each phone call
- Time from randomisation date to date of first hospital admission as recorded at each phone call

Hospital attendance for wheeze:

- Number of hospital attendances (A&E) over the 12 month period as recorded at each phone call
- Time from randomisation date to date of first hospital attendance (A&E) as recorded at each phone call

Unscheduled GP visit for wheeze:

- Number of unscheduled GP visits over the 12 month period as recorded at each phone call
- Time from randomisation date to date of first unscheduled GP visit as recorded at each phone call

**Description of wheezing episodes**

Wheeze:

- Number of wheeze episodes\* as recorded on the diary card
- Time to first episode\* of wheeze as recorded on the diary card
- Duration of wheeze episodes\* as recorded on the diary card

Cold

- Number of cold episodes\* as recorded on the diary card
- Time to first episode\* of cold as recorded on the diary card
- Duration of cold episodes\* as recorded on the diary card

**\*Definition of episode of wheeze and cold: The duration of an episode is defined as the days from the start of symptoms until the last days of symptoms (includes both start and stop day) followed by a period of 5 symptom free days.**

**Medication use**

Steroids (OCS):

- The number of courses per year (and total number of days) as recorded on the diary card. Each mention of use on a separate diary card indicates a course.
- The proportion receiving none vs. any during the trial as recorded on the diary card or in the phonecall data.

Steroids (ICS):

- Proportion starting ICS during the trial as recorded on the diary card or phonecall data (baseline data (T2) indicates whether child was on ICS at the start of the trial)

Salbutamol:

- Total number of puffs overall per episode of wheeze as recorded on the diary card
- Total number of puffs (Salbutamol use per year)

#### Investigational Medicinal Product (IMP) usage:

- The number of IMP initiations (whether for wheeze or cold).
- Mean sachets (IMP use) per episode (wheeze or cold) as recorded on the diary card
- Compliance calculated from diary card, number dispensed and number returned

#### **Inflammatory outcomes**

- Baseline and exit urinary eicosanoid level
- Leukotriene genes (approximately 150 genes)

**Note:** this data is not stored on the main trial database and the analysis is not included within this plan

#### **Safety outcomes**

- The number of withdrawals from the trial per group
- Serious adverse events per group
- Adverse events per group
- All cause mortality per group
- Mortality due to exacerbation of asthma per group
- Mortality due to respiratory infection per group

#### **Economic outcomes**

##### Costs due to wheeze:

Unit costs will be assigned for the cost of medical attendances, medicines and time off work. The analysis of economic and qualitative outcomes is not contained within this analysis plan.

## **STUDY METHODS**

### **Overall study design and plan**

Target for randomisation: 650 intervention and 650 control participants

Date of first randomisation: 25/10/2010

Date of last randomisation: 27/12/2012

Trial design: Individually randomized, parallel group

Blinding: Participants and their treating clinician are blind to treatment allocation

Randomised Interventions: Montelukast vs. placebo

Allocation ratio: 1:1

### **Selection of study population**

#### **Inclusion Criteria**

- age  $\geq$  10 months and  $\leq$  5 years on the day of consent.
- two or more attacks of parent-reported wheeze.
- at least one attack with wheeze validated by a clinician

- the most recent attack within the last 3 months.
- contactable by telephone and able to attend one face-to-face review
- parent or guardian able to give written informed consent for their child to participate in the study.

### **Exclusion Criteria**

- any other chronic respiratory condition diagnosed by a clinician including structural airway abnormality (e.g. floppy larynx) and cystic fibrosis
- any chronic condition that increases vulnerability to respiratory tract infection such as severe developmental delay with feeding difficulty or sickle cell disease
- history of neonatal chronic lung disease
- current continuous oral montelukast therapy
- in a trial using an IMP in the previous 3 months prior to recruitment.

### **Method of treatment assignment and randomisation**

Randomisation was stratified according to ALOX5 promoter polymorphism status. This yielded two groups:

**Group I** Children with the [5/5] ALOX5 promoter polymorphism genotype.

**Group II** Children with [5/x and x/x]" ALOX5 promoter polymorphism genotype; where x is > or < than 5 SP1 repeats.

Children (participants) in each of these two genotype groups were assigned consecutive randomisation numbers from randomised permuted blocks of 10. Within each block equal numbers of children were randomly allocated to placebo and active treatment. When all numbers from the first block had been assigned a new block of randomisation numbers was allocated to that genotype group, until a total of 1300 children in groups 1 and 2 combined had been assigned a randomisation number. If a randomisation number was assigned to a child who did not subsequently take any dose of IMP, the IMP bearing that randomisation number was returned to pharmacy, and the randomisation number may have been assigned to another child (participant).

### **Treatment masking (Blinding)**

This was a double-blind trial: neither subject nor investigator was aware of a subject's allocation. Active and placebo batches of IMP had identical packaging, labelling and appearance.

### **Sample size determination**

This trial is powered to detect a clinically significant difference in the number of attacks of wheeze between intervention and control arms. We also had power to detect large differences responsiveness (in terms of the primary outcome) to montelukast in the stratum with ALOX5 promoter polymorphism [5/5], compared with the stratum with the ALOX5 [5/x and x/x]" genotype.

Data on mean (0.76) and standard deviation (1.22) of number of attacks come from data from the UK General Practitioner Research Database on courses of oral steroids (a proxy for number of episodes). These data follow an overdispersed Poisson distribution. To take account of this we used markov chain Monte Carlo simulation in WinBUGS to estimate sample sizes required: (WinBUGS Version 1.4. 2003 Available from: <http://www.mrc-bsu.cam.ac.uk/bugs/welcome.shtml>). To detect

a 33% drop in attack rate requiring medical attention, with a power of 90% and at a significance level of 5%, and a 6% loss to follow up, we require 1050 children in total. A 33% drop in attack rates equates to an attack rate of 0.51 for the treatment group. The clinical significance of these changes is that approximately four children will need to be treated to prevent one clinically severe attack. A sample size of 1200 gives just over 80% power at the 5% significance level to detect an interaction between treatment and genotype if the effect is a 60% reduction in the [5/x plus x/x] and a 20% reduction in the [5/5] stratum. Assuming a 6% dropout, 1300 children will need to be recruited.

## **DATA COLLECTION**

### **Baseline**

#### ***Demographics***

Height in cm

Weight in Kg

Age in years

Sex (Male; Female)

Stratum (A or B)

Ethnicity (Asian or Asian British; Mixed; Black or Black British; White; Other)

#### ***Risk factors: Birth, Atopy and Family History (Yes, No)***

Preterm birth <37 wk gestation; Birth weight <2500g; Food allergy; Drug allergy; itchy rash for >6 months; Eczema; Tobacco exposure in utero; Tobacco exposure in household; daycare attendance; immunisation status for Pneumococcus; immunisation status for influenza; history of asthma mother; history of asthma father.

#### ***Pre-study illness and therapy (Yes/No)***

Episodic wheeze; multitrigger wheeze; admitted to hospital in last year; ever admitted to hospital; Preventer therapy none; Preventer therapy antileukotriene; Preventer therapy Maintenance inhaled steroids; Preventer therapy episodic inhaled steroids

Age at first wheeze in months

Interval between onset of URTI and wheezing (hours)

Number of courses of systemic steroids in the last year

Number of unscheduled medical attendances for wheeze in last year

#### ***Pre-existing conditions***

Medical condition

Date of diagnosis

Resolved/ongoing

Current treatment

### **Follow up**

#### ***Unscheduled medical attendance***

Phone call data: Type of attendance (A&E; Hospital; GP; Pharmacist; Other)

Phone call data: Duration of visit (calculated from date of admission and date of discharge)

#### ***Description of wheezing episodes***

Diary card: Wheeze in the last 24 hours (Yes/No)

Diary card: Date of diary card entry

Diary card: Duration of wheeze episodes will be calculated where wheeze in the last 24 hours has been ticked over consecutive days

Diary card: Total duration of wheeze days over follow-up period

